6.5.2. Basal Insulin Therapy

During the lead-in period (Visits 2 to 3), participants will continue their prestudy basal and prandial insulin therapy.

At Visit 3, participants will be randomized to study basal insulin LY3209590 or degludec. Basal insulin is titrated based on the FBG target of 80 to 120 mg/dL (4.4 to 6.6 mmol/L) and hypoglycemia evaluation. CGM data including 24-hour glucose profiles and additional SMBG monitoring (if applicable) should also be considered.

Titration of the study basal insulin (LY3209590 or degludec) dose should be made at **weekly** intervals from **Weeks 0 to 12** (titration period, Visits 3 to 15), and then at a minimum of **every 4 weeks** from **Weeks 12 to 52** (Visits 16 to 29) or more often as clinically indicated.

Decreases to the basal insulin dose may be made at any time during the study based upon the judgment of the investigator, for example, in response to hypoglycemia. The basal insulin dose may be influenced by other clinical circumstances and safety considerations known to the investigator; thus, the prescribed basal insulin dose during the study is determined by, and the responsibility of, the investigator.

Participants will measure FBG using the e-diary-linked, study-provided glucometer as described in Section 8.1.1.1. The median FBG for basal insulin dose adjustment is obtained from the 3 most recent FBGs in the previous week. The median is the middle value when the 3 values are placed in ascending or descending order. For example, if a participant's FBGs for the past week measurements were 132, 140, and 128, the median is 132. Investigators should also consider CGM data for basal insulin dose titration.

Note: If the participant has only 2 FBG readings for the week, then the lesser of the readings should be used to determine the dose adjustments. If only 1 FBG measurement is available, determination if dose is changed using only a single FBG value is at the discretion of the investigator.

6.5.2.1. LY3209590 Dose Initiation and Modification

This section outlines LY3209590

- loading dose (Week 0)
- starting weekly dose (Week 1)
- weekly dose (Weeks 2 to 52)
- dose modification guidance based on hypoglycemia, and
- dose modification guidance based on FBG.

Visit 3 (Week 0 – Randomization) loading dose

At Visit 3 (Week 0), participants randomized to LY3209590 will start study basal insulin therapy.

The LY3209590 **loading dose** is administered at the site and is based on the participant's prior daily basal insulin dose and median FBG from the week prior to randomization (Visit 3 [Week 0]).

Note: If the participant's prestudy basal insulin is **glargine U-300**, the prior daily basal insulin dose should be **reduced by 20%** when determining usual daily basal insulin dose.

For participants with **median FBG \leq 140 mg/dL (7.8 mmol/L)**, follow instructions in this table to calculate the LY3209590 Loading Dose.

LY3209590 Loading Dose – Participants with Median FBG \leq 140 mg/dL (7.8 mmol/L)		
Step	Action	Example Participant A FBG \leq 140 mg/dL (7.8 mmol/L)
1	Determine usual daily basal insulin dose from the lead-in period	24 units/day
2	Calculate Starting Weekly Dose (daily basal dose multiplied by 7 and round to nearest 10)	170 units/week
3	Multiply Starting Weekly Dose by 3 to determine the Loading Dose	510 units Loading Dose

For participants with FBG > 140 mg/dL (7.8 mmol/L), an incremental addition to the prior daily basal insulin dose was instituted to reduce transient hyperglycemia while LY3209590 achieves steady state.

For participants with **median FBG 141 to 160 mg/dL (>7.8 to 8.9 mmol/L)**, the prior daily basal insulin dose should be increased by **10 to 20%**. Follow instructions in this table to calculate the LY3209590 Loading Dose.

LY3209590 Loading Dose – Participants with Median FBG 141 to 160 mg/dL (7.8 to 8.9 mmol/L)		
Step	Action	Example Participant B FBG 141 to 160 mg/dL (>7.8 to 8.9 mmol/L)
1	Determine usual daily basal insulin dose from the lead-in period	24 units/day
2	Increase the usual daily basal insulin dose by 10 to 20% to determine the adjusted daily basal dose	26 units/day
3	Calculate Starting Weekly Dose (adjusted daily basal dose multiplied by 7 and round to nearest 10)	180 units/week
4	Multiply Starting Weekly Dose by 3 to determine the Loading Dose	540 units Loading Dose

For participants with **median FBG >160 mg/dL (8.9 mmol/L)**, the prior daily basal insulin dose should be increased by **20 to 30%**. Follow instructions in this table to calculate the LY3209590 Loading Dose.

LY3209590 Loading Dose – Participants with Median FBG >160 mg/dL (8.9 mmol/L)		
Step	Action	Example Participant C FBG >160 mg/dL (>8.9 mmol/L)
1	Determine usual daily basal insulin dose from the lead-in period	24 units/day
2	Increase the usual daily basal insulin dose by 20 to 30% to calculate the adjusted daily basal dose	30 units/day
3	Calculate Starting Weekly Dose (adjusted daily basal dose multiplied by 7 and round to nearest 10)	210 units/week
4	Multiply Starting Weekly Dose by 3 to determine the Loading Dose	630 units Loading Dose

Visit 4 (Week 1) starting weekly dose

The **Starting Weekly Dose** (Week 1) is administered at the site at Visit 4

If the participant experienced hypoglycemia in the previous week and met any of the criteria for a dose reduction as listed in the hypoglycemia dose reduction for LY3209590 table below, the Visit 4 starting weekly dose may be reduced by 10% or as clinically indicated.

CAUTION: Do NOT repeat administration of the loading dose.

Visits 5 to 29 (Weeks 2 to 52) weekly dosing

Titration of the study basal insulin LY3209590 dose should be made at weekly intervals from Weeks 0 to 12 (titration period, Visits 3 to 15), and then at a minimum of every 4 weeks from Weeks 12 to 52 (Visits 16 to 29) or more often as clinically indicated.

Assess hypoglycemia events over the previous week.

Reduce the LY3209590 dose if the participant meets criterion for hypoglycemia dose reduction according to this table.

Hypoglycemia Dose Reduction Criteria	Decrease the LY3209590 Dose
2 nocturnal hypoglycemia events ≤ 70 mg/dL ^a (3.9 mmol/L)	
2 fasting hypoglycemia events ≤ 70 mg/dL ^a (3.9 mmol/L)	to previous lower dose ^b
1 nocturnal and 1 fasting hypoglycemia event ≤ 70 mg/dL ^a (3.9 mmol/L)	
Any confirmed severe hypoglycemia	by 20 to 40 units or as clinically indicated

^a Investigator should use discretion to adjust for daytime hypoglycemia that is not attributed to prandial insulin.

^b If there is no previous lower dose, then decrease basal insulin dose by 10% or as clinically indicated.

If the participant does not meet criteria for hypoglycemia dose reduction, determine the median fasting glucose and adjust the LY3209590 dose according to this table.

LY3209590 Dose Adjustment			
Median FBG (mg/dL)	Median FBG (mmol/L)	LY3209590 Dose <100 Units per Week	LY3209590 Dose ≥100 Units per Week
<80	<4.4	Decrease to previous lower dose ^a	Decrease to previous lower dose ^a
80-120	4.4-6.6	No change	No change
121-150	6.7-8.3	Increase by 5 units	Increase by 10 units
151-180	8.4-10.0	Increase by 10 units	Increase by 20 units
>180	>10.0	Increase by 20 units	Increase by 30 units

^a If there is no previous lower dose, then decrease basal insulin dose by 10% or as clinically indicated.

6.5.2.2. Insulin Degludec Dose Initiation and Modification

This section outlines insulin degludec

- dose initiation at Visit 3 (Week 0)
- dose modification guidance based on hypoglycemia, and
- dose modification guidance based on FBG.

Visit 3 (Week 0 – Randomization)

At Visit 3 (Week 0), participants randomized to insulin degludec will start study basal insulin therapy.

The initial degludec dose may be unit-for-unit of the prior basal insulin regimen.

Note: If the participant's prestudy basal insulin is **glargine U-300**, reduce the prior basal insulin dose by **20%**.

Visits 4 to 29 (Weeks 1 to 52)

Titration of the study basal insulin degludec dose should be made at weekly intervals from Weeks 0 to 12 (titration period, Visits 3 to 15), and then at a minimum of every 4 weeks from Weeks 12 to 52 (Visits 16 to 29) or more often as clinically indicated.

Assess hypoglycemia events over the previous week.

Reduce the insulin degludec dose if the participant meets criterion for hypoglycemia dose reduction according to this table.

Hypoglycemia Dose Reduction Criteria	Decrease the Insulin Degludec Dose
2 nocturnal hypoglycemia events ≤ 70 mg/dL ^a (3.9 mmol/L)	
2 fasting hypoglycemia events ≤ 70 mg/dL ^a (3.9 mmol/L)	to previous lower dose ^b
1 nocturnal and 1 fasting hypoglycemia event ≤ 70 mg/dL ^a (3.9 mmol/L)	
Any confirmed severe hypoglycemia	by 2 to 6 units or as clinically indicated

^a Investigator should use discretion to adjust for daytime hypoglycemia that is not attributed to prandial insulin.

^b If there is no previous lower dose, then decrease basal insulin dose by 10% or as clinically indicated.

If the participant does not meet criteria for hypoglycemia dose reduction, determine the median fasting glucose and adjust the insulin degludec dose according to this table.

Insulin Degludec Dose Adjustment			
Median FBG (mg/dL)	Median FBG (mmol/L)	Degludec Dose <15 Units per Day	Degludec Dose ≥ 15 Units per Day
<80	<4.4	Decrease to previous lower dose ^a	Decrease to previous lower dose ^a
80-120	4.4-6.6	No change	No change
121-150	6.7-8.3	Increase by 1 unit	Increase by 2 units
151-180	8.4-10.0	Increase by 2 units	Increase by 3 units
>180	>10.0	Increase by 3 units	Increase by 4 units

^a If there is no previous lower dose, then decrease basal insulin dose by 10% or as clinically indicated.

Source: Adapted from Bartley et al. 2008 and Bolli et al. 2009.

6.5.3. Prandial Insulin Therapy

During the lead-in period (Visits 2 to 3), participants will continue their prestudy basal and prandial insulin therapy.

During the treatment period (Visits 3 to 29), all participants will be treated with insulin lispro. The initial insulin lispro doses may be unit-for-unit of the prestudy prandial insulin regimen.

Prandial insulin is titrated based on glucose and hypoglycemia data from CGM and SMBG. Decreases to the prandial insulin dose may be made at any time during the study based upon the judgment of the investigator, for example, in response to hypoglycemia. The prandial insulin dose may be influenced by other clinical circumstances and safety considerations known to the investigator; thus, the prescribed prandial insulin dose during the study is determined by, and the responsibility of, the investigator.

The investigator, in consultation with the participant, will determine the prandial dosing plan to use during the study. The following prandial dosing plans may be considered:

- Carbohydrate-counting plan: If the participant performed flexible carbohydrate counting for prandial insulin dosing (insulin to carbohydrate ratio plan) prior to study enrollment, this plan may be continued during the study. The prandial insulin dose is based on the participant's estimated carbohydrate content of the meal, such as unit insulin per grams carbohydrate.
- Fixed-dose plan: The participant is prescribed a fixed dose or dose range of insulin for each meal. The fixed dose or dose range of insulin may be individualized for each meal.

The participant should maintain the same prandial insulin dosing plan throughout the study.

Correction factor, for example, 1 unit of insulin per glucose (mg/dL or mmol/L) above target goal, may be implemented with either prandial insulin dosing plan.

For participants who are using the **carbohydrate-counting plan**: the insulin to carbohydrate ratio, and correction factor if applicable, should be reviewed and adjusted by the investigator, in discussion with the patient, based on CGM, SMBG, and hypoglycemia data at clinic and telephone visits and as clinically indicated. Twenty-four-hour glucose profiles, including premeal glucose and postprandial glucose levels, from CGM can be evaluated.

For participants who are using the **fixed-dose plan**: the prandial insulin dose, and correction factor if applicable, should be reviewed and adjusted by the investigator, in discussion with the patient, based on CGM, SMBG, and hypoglycemia data at clinic and telephone visits and as clinically indicated. Twenty-four-hour glucose profiles, including premeal glucose and postprandial glucose levels, from CGM can be evaluated.

In the fixed-dose plan, assessment of the prandial insulin dose may include review of the pattern of CGM glucose levels from the previous week or as clinically indicated for the corresponding meal or bedtime as described in the table below.

For example, if assessing the need to adjust the morning meal prandial insulin dose, review the CGM glucose values from the previous week pre-mid-day meal.

Prandial Insulin Dose Assessed	Corresponding CGM Glucose for Review
Fasting or morning premeal	Pre-midday meal glucose values
Midday premeal	Pre-evening meal glucose values
Evening premeal	Bedtime glucose values

Abbreviation: CGM = continuous glucose monitoring.

The pattern of CGM glucose values from the premeal or bedtime is used as the “adjustment value” and the change in dose, either increase or decrease, is based upon this value as described in the table below.

If Meal Time Dose of Insulin Lispro is	Pattern of CGM Glucose Below Target Range	Pattern of CGM Glucose at Target Range	Pattern of CGM Glucose Above Target Range
≤10 units	Decrease by 1 unit	No change	Increase by 1 unit
11-19 units	Decrease by 1-2 units	No change	Increase by 1-2 units
≥20 units	Decrease by 2-3 units	No change	Increase by 2-3 units

Source: Adapted from Bergenstal et al. 2008.

For either prandial insulin dosing plan, the investigator may determine the appropriate **correction factor** for the participant to administer when premeal glucose levels are above target based on clinical judgment, taking into account the participant’s clinical history, insulin regimen, and recent glucose profiles. Alternatively, the correction factor may initially be calculated as follows:

correction factor = 1800/total daily insulin dose = estimated decrease in glucose (mg/dL) level per unit of prandial insulin administered, or

correction factor = 100/total daily insulin dose = estimated decrease in glucose (mmol/L) level per unit of prandial insulin administered.

6.6. Continued Access to Study Intervention after the End of the Study

The sponsor will not provide participants with ongoing supplies of study intervention after they have completed the study treatment period or permanently discontinued the study intervention.

6.6.1. Transitioning off of Study Basal Insulin

At the last treatment visit (Visit 29 [Week 52] or ET visit), the investigator will prescribe a non-study basal insulin for use during the safety follow-up period.

The investigator, in consultation with the participant, will decide on prandial insulin therapy for use during the safety follow-up period.

Study participants treated with LY3209590

Participants will administer their last dose of LY3209590 at Week 51 of the study and can begin the transition to the non-study insulins after Visit 29 (Week 52). At Visit 29 (Week 52), the investigator will review instructions for transitioning to the non-study insulins with the participant. The non-study daily basal insulin treatment should be started slowly and under regular review of glucose profiles after discontinuation of LY3209590.

Since LY3209590 has a half-life of approximately 17 days, a slow up-titration of the non-study daily basal insulin is necessary to prevent hypoglycemia due to overlapping insulin action. Non-study basal insulin would not be required until the study participant's fasting glucose is above 100 mg/dL (5.5 mmol/L), and then daily basal insulin would be initiated and adjusted based on fasting glucose, CGM profile, and hypoglycemia evaluation. The investigator should consider titration of the non-study basal insulin to reach 50% of the required daily basal insulin dose at approximately 2 weeks and 80% of the required daily basal insulin dose at approximately 4 weeks. An unscheduled visit in addition to Visit 801 may occur during this time to facilitate the transition to non-study daily basal insulin.

Study participants treated with insulin degludec

Participants assigned to the insulin degludec treatment arm will transition to their non-study basal insulin after Visit 29 (Week 52) with dose adjustment per investigator discretion based on fasting glucose, CGM profile, and hypoglycemia evaluation and in accordance with the local product label for the basal insulin.

6.7. Treatment of Overdose

Study intervention overdose, dangerously large amount of insulin compared to the protocol-prescribed dose, will be reported as per Section 10.3.1. In the event of an overdose, refer to the IB for LY3209590 or product label for insulin degludec depending on the participant treatment assignment.

In the event of an overdose, the investigator/treating physician should

- Contact the medical monitor immediately.
- Evaluate the participant to determine, in consultation with the medical monitor, whether study intervention should be interrupted or whether the dose should be reduced.
- Closely monitor the participant for any AE/SAE and laboratory abnormalities until study intervention no longer has a clinical effect
- Obtain a plasma sample for PK analysis if the participant is assigned to LY3209590.

6.8. Concomitant Therapy

Concomitant therapy regimens

All participants should maintain their usual medication regimens for concomitant conditions or diseases throughout the study, unless those medications are specifically excluded in the protocol (Section 5.2).

Changing concomitant therapy

Participants should consult with authorized study personnel before taking any new medications during the study, except when initiated for treatment of medical emergencies. Authorized study personnel should consult the sponsor's medical monitor if there are any questions about concomitant therapies during the study.

Concomitant therapy data collection

For therapy that the participant is receiving at the time of enrollment or receives during the study, including over-the-counter medications, authorized study personnel should collect

- the name of medication, vaccine, or therapy
- the reason for use, and
- dates of administration, including start and end dates.

Non-study medications taken by study participants who have signed informed consent, but are not randomized to study insulin, will not be reported unless an SAE or AE occurs that the investigator believes may have been caused by a study procedure.

Excluded concomitant medications

The following concomitant therapies will not be allowed during the study:

- any oral or injectable medication intended for the treatment of diabetes mellitus other than study insulins

Exception: Short-term use of non-study insulins is permissible as outlined in Section 7.1.3.

Note: Participants who require treatment with non-study basal insulins as rescue therapy for management of severe or persistent hyperglycemia as outlined in Section 6.1.3., must discontinue study basal insulin therapy (LY3209590 or insulin degludec). The participant will remain in the study and follow procedures for the remaining study visits.

- chronic (lasting longer than 14 consecutive days) systemic glucocorticoid therapy excluding topical, intraocular, intranasal, inhaled, or intraarticular preparations, and
- weight loss drugs, for example, prescription drugs: glucagon-like peptide-1 (GLP-1) receptor agonists, lorcaserin, orlistat, phentermine, phentermine and topiramate combination, naltrexone and bupropion combination, or over-the-counter weight loss medications.

7. Discontinuation of Study Intervention and Participant Discontinuation/Withdrawal

Discontinuation of specific sites or of the study as a whole are handled as part of Appendix 1.

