20. Have known hemoglobinopathy, hemolytic anemia, sickle cell anemia, or any other hemoglobin abnormalities known to interfere with the measurement of HbA1c in the opinion of the investigator.

Malignancy

21. Have a history of an active or untreated malignancy or are in remission from a clinically significant malignancy within 5 years prior to screening.

Exceptions:

- basal cell or squamous cell skin cancer.

22. Are at increased risk for developing cancer or a recurrence of cancer.

General

23. Have had a significant weight gain or loss in the past 3 months in the investigator's opinion, for example, $\geq 5\%$.
24. Have known hypersensitivity or allergy to any of the study medications or their excipients.
25. Have any other serious disease or condition that, in the opinion of the investigator, would pose a significant risk to the study participant or preclude the study participant from following and completing the protocol.
26. Are women who test positive for pregnancy or intend to become pregnant.
27. Are women who are lactating or breastfeeding.

Prior or concomitant therapy

28. Have been on an insulin treatment regimen, including NPH insulin, U-500 insulin, regular human insulin, or any premixed insulins within 90 days prior to screening.

29. Have used insulin human inhalation powder (Afrezza) within 90 days prior to screening.
30. Have used continuous subcutaneous insulin infusion therapy within 90 days prior to screening.
31. Are receiving any oral or injectable medication intended for the treatment of diabetes mellitus other than insulins as specified in Inclusion Criterion 4 in the 90 days prior to screening.
32. Are receiving chronic (>14 days) systemic glucocorticoid therapy or have received such therapy for >14 days within 30 days prior to screening.

Exceptions:

- replacement therapy for adrenal insufficiency, and
- topical, intraocular, intranasal, or inhaled preparations or intra-articular injection

33. Have used any weight loss drugs within 90 days prior to screening.

Examples:

- glucagon-like peptide-1 (GLP-1) receptor agonists
- lorcaserin
- orlistat
- phentermine
- phentermine and topiramate combination
- naltrexone and bupropion combination, or
- over-the-counter weight loss medications.

Prior or concurrent clinical study experience

34. Are currently enrolled in any other clinical study involving an intervention or any other type of medical research, judged not to be scientifically or medically compatible with this study.

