7.2. Participant Discontinuation/Withdrawal from the Study

Discontinuation is expected to be uncommon.

A participant may withdraw from the study:

- at any time at the participant's own request
- at the request of the participant's designee (for example, parents or legal guardian)
- at the discretion of the investigator for safety, behavioral, compliance, or administrative reasons
- if enrolled in any other clinical study involving an investigational product, or enrolled in any other type of medical research judged not to be scientifically or medically compatible with this study
- if the participant, for any reason, requires treatment with a therapeutic agent that is prohibited by the protocol and has been demonstrated to be effective for treatment of the study indication. In this case, discontinuation from the study occurs prior to introduction of the new agent, and
- if a study participant is diagnosed with any type of diabetes mellitus other than T1D.

At the time of discontinuing from the study, if possible, the participant will complete procedures for an early discontinuation visit and post-treatment follow-up, if applicable, as shown in the SoA.

If the participant has not already discontinued the study intervention, the participant will be permanently discontinued from the study intervention at the time of the decision to discontinue the study.

If the participant withdraws consent for disclosure of future information, the sponsor may retain and continue to use any data collected before such a withdrawal of consent.

If a participant withdraws from the study, the participant may request destruction of any samples taken and not tested, and the investigator must document this in the site study records.

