6.5. Appendix 5: Protocol Deviations

Important protocol deviations (IPDs) are the deviations from the study protocol that may compromise the data integrity and participants' safety. The IPD categories and details of IPD identification are provided in the trial issue management plan.

The number and percentage of participants with any reported IPDs will be summarized by treatment group and IPD category. The IPDs identified by site monitoring and clinical database will be integrated. If the IPD is identified by both methods, only the site monitoring IPD will be presented.

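### Section 6.8 drops the adrenal-replacement exception that exclusion criterion 32 makes, so it bans during the study a therapy the protocol admits at entry

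*Protocol*

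**What the plan says.** Three pieces of protocol text bear on this.

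- **Entry (Section 5.2, criterion 32).** People are excluded if they "Are receiving chronic (>14 days) systemic glucocorticoid therapy or have received such therapy for >14 days within 30 days prior to screening". Two exception bullets follow. The first is "replacement therapy for adrenal insufficiency". The second covers five local routes: topical, intraocular, intranasal, inhaled and intra-articular.
- **General rule on study (Section 6.8, opening sentence).** Everyone enrolled is told to "maintain their usual medication regimens for concomitant conditions or diseases throughout the study, unless those medications are specifically excluded in the protocol (Section 5.2").
- **Prohibited list on study (Section 6.8, excluded concomitant medications).** Among the therapies not permitted is "chronic (lasting longer than 14 consecutive days) systemic glucocorticoid therapy excluding topical, intraocular, intranasal, inhaled, or intraarticular preparations". Adrenal replacement is not among the exceptions.

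Section 6.8 also tells study personnel to consult the sponsor's "medical monitor if there are any questions about concomitant therapies during the study".

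**The concern.** A person on long-term adrenal replacement can pass criterion 32, be randomised, and from the first day be taking something the Section 6.8 list disallows. Section 6.8 then conflicts with itself: its opening sentence, read with Section 5.2, says to continue the therapy, and the bullet says it may not be used.

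The stakes are operational and clinical. Sites may resolve the conflict differently. Monitors may record deviations for a therapy the protocol chose to admit. SAP Section 6.5 states: "The number and percentage of participants with any reported IPDs will be summarized by treatment group and IPD category". Such entries would reach that summary only if the trial issue management plan, which is not among the documents, counts prohibited concomitant therapy as important. There is also a small risk that a site changes essential replacement therapy because of the bullet.

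**Working it through.** There is no planned figure to reproduce. The check is a comparison of two lists.

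| Exception to the chronic systemic glucocorticoid rule | Criterion 32 (Section 5.2) | Section 6.8 bullet |
|---|---|---|
| Replacement for adrenal insufficiency | yes | **no** |
| Topical | yes | yes |
| Intraocular | yes | yes |
| Intranasal | yes | yes |
| Inhaled | yes | yes |
| Intra-articular | yes | yes |

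Criterion 32: 1 indication + 5 routes = 6 exceptions. Section 6.8: 5. Missing: 6 − 5 = 1. Counted by bullet, criterion 32 has two and Section 6.8 carries over one. The result is the same.

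**Does the ban reach replacement therapy?** Yes. Criterion 32 lists adrenal replacement as an exception to systemic glucocorticoid therapy, so the protocol itself places it within that term. Section 6.8 uses the same term with the same 14-day threshold.

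**Is the exception restored elsewhere?** No. Neither the discontinuation rules in Sections 7.1 and 7.2 nor the amendment history does so.

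**Does any rule require the therapy, study drug or participation to stop?** No. The permanent-discontinuation list in Section 7.1 does not name prohibited concomitant therapy. The prohibited-agent rule in Section 7.2 applies only to an agent that is "prohibited by the protocol and has been demonstrated to be effective for treatment of the study indication", which a glucocorticoid is not.

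**Slip or policy?** The neighbouring weight-loss bullet in Section 6.8 repeats all 7 examples given in criterion 33, which suggests that the entry lists were being copied across. This is weak support, because those are examples of banned drugs and not exceptions. The pointer to Section 5.2 in the opening sentence is stronger evidence of a slip.

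**Size.** One affected participant is 1/670 = 0.15% of the planned sample. This is a unit, not an estimate of how many are affected. No prevalence is given and none is assumed.

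**The case against.** The strongest reply is that the intended instruction can be recovered. Section 6.8 defers to Section 5.2, which specifically exempts replacement, and a specific exception should prevail over a less complete restatement of the same rule. A site in doubt can ask the medical monitor. No stopping rule or analysis rule is triggered. The deviation argument rests on a plan that is not available, and the safety argument needs an investigator to act against the opening sentence without asking. The number affected could be zero.

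Much of this stands. It shows what was meant, and it limits the consequences to possible rather than demonstrated ones. It does not change the wording of the ban, and a flat prohibition gives a site no evident reason to ask. The appeal to the opening sentence also leaves a gap: that sentence protects usual regimens, and criterion 32 governs entry. If adrenal insufficiency is diagnosed during the 52-week treatment period, the bullet is the only text that addresses chronic glucocorticoids, and it forbids them.

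**Conclusion.** The concern holds. One of six exceptions is missing from an operative list, and as written that list bars an essential therapy in people the protocol admits. The omission is certain from the text. That it was unintended is an inference, though a strong one. The consequences are expected to be small and depend on how many participants, if any, take or start adrenal replacement. Sample size, power, type I error control and both estimands are unaffected: the only intercurrent events defined are treatment discontinuation and initiation of rescue medication. The correction is worth making because the present wording is wrong on a point of participant safety and the remedy costs almost nothing.

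**What to change.** In the glucocorticoid bullet of Section 6.8, add "replacement therapy for adrenal insufficiency" to the exceptions. Alternatively, delete the restated list and write: except as listed in exclusion criterion 32. Either way all 6 of 6 exceptions match, and the same list governs entry and the treatment period. With the cross-reference, make clear that it also covers replacement started after randomisation.

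The cost is one phrase in the next amendment or a clarification letter to sites. Nothing changes in the sample, the procedures or the SAP.
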